3 STUDY OBJECTIVES AND DESIGN

3.1 Hypothesis, primary and secondary objectives

The **Null hypothesis (H₀)** describes no difference in functional outcome rates of early minimally invasive image-guided endoscopic evacuation additionally to BMT for SSICH compared to BMT alone.

The **Alternative Hypothesis (H₁)** describes a difference (either improved or worsened [two-sided testing]) functional outcome rates of early minimally invasive image guided endoscopic evacuation additionally to BMT for SSICH compared to BMT alone.

The primary objective of this two, armed, open-labelled, single centre randomised controlled trial is to show superiority of early minimally invasive image-guided hematoma evacuation additionally to BMT compared to BMT alone in functional outcome rates at 6 months in patients with SSICH.

Secondary objectives are:

- to show superior survival rates of patients in the ES arm
- to study patient reported quality of life after treatment for SSICH at different time points (3 and 6 months after intervention)
- to study patient satisfaction with the outcome after treatment for SSICH at different time points (3 months and 6 months after intervention)
- to study cognitive outcome in patients after treatment for SSICH at different time points (3 months and 6 months after intervention)
- to study the morbidity rates of patients in both treatment arms
- to study the efficacy of ES in reducing the hematoma volume
- to study the change in focal neurological deficits exhibited by the patients after treatment.
- to study the temporal evolution of serum biomarkers (Neurofilament light-chain subunit (NfL), Glial Fibrillary Acidic Protein (GFAP), S100 calcium-binding protein B (S100B), IL-1 α and β , IL-2, IL-4, IL-5, IL-6, IL-8, IL-10, IL-12p70 and TNF- α) and their change in relation to early hematoma ES.

3.2 Primary and secondary outcomes

Primary outcome:

- Good functional outcome 6 months after treatment, measured by the mRS[33]. Good functional outcome is defined as a mRS of ≤ 3 points and will be assessed as binary outcome (yes/no, final value) at 6 months after treatment. The cut-off for good functional outcome is chosen at a mRS score of 3 points, as this reflects the turning point for a patient being able to live a partially self-dependent life or to live a severely disabled life. In this context, a mRS score of 3 points reflects the ability to walk unassisted and care for one's own bodily needs despite being moderately dependent on assistance, while a mRS score of 4 points describes a patient who is not able to walk anymore and needs assistance with all daily activities and thus marks a severe loss of patient autonomy.

Secondary outcomes:

- The mortality rate as measured by death of a participant (binary outcome (yes/no), final value) at 6 months after intervention.

- Patient reported outcome measures at 3 and 6 months after intervention, those being:
 - Patient and caregiver quality of life as assessed by the PROMIS® questionnaire (continuous variable, final value)
 - Patient Satisfaction as assessed by a short survey (Appendix 2) on a scale of 1-5 (continuous variable, final value)
 - Patient cognitive outcome as assessed by the MOCA® Test (continuous variable, final value)
- The morbidity rate, meaning occurrence of:
 - Ischemic stroke
 - Recurrent SSICH (defined as any radiologically confirmed increase in hematoma volume postoperative/follow-up that is either asymptomatic or associated with a worsening of the focal-neurological deficit by ≥ 4 points on the NIHSS and/or a decrease in consciousness by ≥ 2 points on the GCS)
 - Epileptic seizure
 - Surgical site infection (intervention group only)
 - Any need for open neurosurgical procedures
 - Infections (i.e. pneumonia, urinary tract infection)
 - Any other not defined complication that prolongs the hospital stay and/or leads to further treatment not envisaged in the original treatment plan.

The occurrence of any of these events 6 months after intervention (binary variable (occurrence/no occurrence), final value, proportion).

- The change of focal neurological deficit measured by the NIHSS, from baseline to 6 months after intervention as a continuous variable (continuous variable, change from baseline).
- The change of disability measured by the mRS, from baseline to 6 months after intervention as a continuous variable (change from baseline, so called mRS shift analysis).
- The time to intervention, defined as the period from symptom onset/last seen well to start of surgery (start surgical measures, i.e. positioning of patient) or start of medical treatment (admission of first treatment of BMT) (continuous variable, time to event).
- The temporal evolution of serum levels of the prespecified biomarkers as continuous variable from start to 6 months after intervention (continuous variable, change from baseline).
- The total time spent on the intensive care unit (ICU)/stroke unit as a continuous variable from the first admission to the ICU/stroke unit to discharge from ICU/stroke unit at 7 days/discharge after intervention (continuous variable, final value).
- The total time spent in intubation measured in minutes from the start of intubation to extubation as specified in the anesthesiology report at 7 days/discharge after intervention (continuous variable, final value).

Outcomes/Measurements applying to the intervention group only:

- The proportion of hematoma volume reduction rate (goal $\leq 15\%$ of its initial volume). The hematoma volume will be measured on serial cranial computer tomography (cCT) and the difference between the volume of the cCT used for surgery and the cCT directly after surgery will be calculated. The hematoma volume on the pre-

operative cCT will be calculated using the $(A * B * C)/2$ method during screening and secondarily validated using the volumetric function of the navigation software[34] Hematoma on directly postoperative images will be calculated using the volumetric function of the navigation software. The hematoma volume reduction rate will be a binary variable (achieved reduction < 15%/did not achieve reduction < 15%, final value).

- The relative (percentage) reduction or increase of hematoma volume from baseline admission cCT to postoperative cCT directly after surgery as a continuous variable (final value).

Additionally, we will collect baseline data of all patients such as age, sex, prior medical history and medication out of the electronic patient file.

Baseline factors acting as confounders and/or effect modifiers potentially influencing the primary and secondary endpoints are: age, existing comorbidities and use of oral anticoagulants (OAC, including Vitamin K Antagonists [VKA], New Oral Anticoagulants [NOAC], Direct Oral Anticoagulants [DOAC]). Correction in the primary outcome analysis will be conducted for; ICH volume, presence of intraventricular haemorrhage, do-not-resuscitate orders, location of haemorrhage and centre.

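### Read literally, the definition of recurrent SSICH counts a silent re-bleed and a severe one, but not one with mild worsening (NIHSS up by 1 to 3 with a GCS fall below 2, or an isolated 1-point GCS fall)

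*Protocol*

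**What the plan says.** Section 3.2 lists a secondary outcome headed "The morbidity rate, meaning occurrence of", followed by seven items. The second is recurrent SSICH. Its imaging condition reads "defined as any radiologically confirmed increase in hematoma volume postoperative/follow-up". A clinical condition then narrows this to an increase "that is either asymptomatic or associated with a worsening of the focal-neurological deficit by ≥ 4 points on the NIHSS", with one further way to qualify: "and/or a decrease in consciousness by ≥ 2 points on the GCS". The Endpoint(s) row of the synopsis gives the same definition in the same words.

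The seventh item is a residual category: "Any other not defined complication that prolongs the hospital stay and/or leads to further treatment not envisaged in the original treatment plan". The outcome is scored as one yes/no variable: "The occurrence of any of these events 6 months after intervention (binary variable (occurrence/no occurrence), final value, proportion".

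The definition sets no minimum size for the volume increase, and no section says what *asymptomatic* means.

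**The concern.** The clause after the imaging condition works as a filter with two ways through: no symptoms, or symptoms above a threshold. Symptoms below both thresholds pass neither. The rule therefore does not rise with severity. As a confirmed re-bleed goes from silent to mild to severe, it is an event, then not an event, then an event again.

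Morbidity in both arms is a stated secondary objective (section 3.1), and bleeding is among the surgical risks named in sections 2.2 and 7.2. Applied as written, the recurrence component omits the middle of the severity range. Event status can also turn on whether a small change is recorded as no symptoms or as one point of worsening. The trial is open-label. Section 3.3.4 describes blinded outcome assessment by telephone at 3 and 6 months, and no blinding is described for the NIHSS and GCS taken during the hospital stay.

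**Working it through.** No figure in the protocol is at stake, so the check is one of logic.

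**Inputs (section 3.2, repeated in the synopsis).** Let V be a radiologically confirmed volume increase, A asymptomatic, N the points of NIHSS worsening and G the points of GCS lost. The definition is:

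recurrent SSICH = V and (A or N ≥ 4 or G ≥ 2)

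**Step 1: literal reading.** Given V, take A to mean no change on either scale (N = 0 and G = 0).

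| NIHSS worsening | GCS fall 0 | GCS fall 1 | GCS fall ≥ 2 |
|---|---|---|---|
| 0 | event (silent) | **not an event** | event |
| 1, 2 or 3 | **not an event** | **not an event** | event |
| ≥ 4 | event | event | event |

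Combinations left out: 3 NIHSS values × 2 GCS values = 6, plus the isolated 1-point GCS fall = 1, so 6 + 1 = 7. The GCS limb matters here: NIHSS worsening of 1 to 3 with a GCS fall of 2 or more is counted. The gap is confined to patients below both thresholds who are not symptom-free.

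**Step 2: the more generous reading.** Suppose *asymptomatic* means below both thresholds, that is, A = not (N ≥ 4 or G ≥ 2). The bracket is then always true and the definition reduces to V, so every confirmed increase counts. The two readings differ in exactly the 7 combinations above. The same patients would give different event counts depending on who applies the rule.

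**Step 3: does another item recover these patients?** The residual item requires a longer stay or unplanned treatment. A patient in the gap who meets that condition, or who has another listed event such as a seizure, an infection or an open procedure, counts in the composite. The composite therefore loses only patients in the gap who have neither. In the recurrent-SSICH component every increase in the gap is lost, because no other item feeds that component.

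**Step 4: size.** If a share s of confirmed increases lies in the gap, the component captures a fraction (1 − s) of them. The protocol gives neither a re-bleed rate nor any basis for s, so no count follows from it.

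**Step 5: what is not touched.** The primary outcome is mRS ≤ 3 at 6 months. The Bayes-factor rule and the maximum of 200 patients rest on that outcome alone. None of them uses this definition.

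**The case against.** The strongest reply is that the sponsor meant a simple two-way split: symptomatic above the thresholds, and everything else. The opening words admit any confirmed increase. Elsewhere the protocol treats re-bleeding as an imaging finding with no symptom filter (V2 in section 4.3.2, the scan footnotes to the visit schedule, section 4.3.7.1). This may well be the intent. It does not settle the matter, because the definition uses an undefined word whose ordinary meaning excludes mild symptoms.

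It is also fair to say that the specified outcome is the composite, that the protocol names no separate analysis of the recurrence component, and that much of the information survives elsewhere. NIHSS change is its own secondary outcome, NIHSS and GCS are recorded at all six visits, and recurrent ICH appears without thresholds in the SAE section (6.2). These points limit the consequence but leave the classification rule wrong.

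A reader might infer three stronger things that the documents do not support:

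- **A number of lost re-bleeds.** Assuming that 10 to 20% of 200 patients re-bleed and 20 to 40% of those fall in the gap gives 200 × 0.10 × 0.20 = 4 to 200 × 0.20 × 0.40 = 16. Neither input is in the protocol, and the resulting share lost is simply the second assumption restated.
- **That re-bleeding is the leading hazard of the procedure.** Sections 2.2 and 7.2 list bleeding beside infection, anaesthetic complications and damage to brain structures, without ranking them.
- **That the gap would favour surgery.** An arm whose re-bleeds moved from silent to mildly symptomatic would show fewer recurrences, but nothing in the protocol suggests that either treatment does this.

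**Conclusion.** The point holds as a defect in a stated rule. As worded, the definition leaves out confirmed re-bleeds with mild worsening while counting silent ones, and no other section closes the gap. It rests on the ordinary meaning of *asymptomatic*; under the generous reading the gap disappears, but the text does not give that reading.

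The reach is limited to one of seven components of a secondary composite, which recaptures some of these patients through its other items. The number affected cannot be derived from the protocol. The definition should be corrected before events are classified, but it does not threaten the trial's main conclusion.

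**What to change.** In section 3.2 and in the synopsis, with matching words:

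- Count any radiologically confirmed increase in hematoma volume as recurrent SSICH, regardless of symptoms. Add no further undefined qualifier.
- Grade each recurrence as symptomatic (NIHSS worsening of at least 4 and/or a GCS fall of at least 2, the protocol's own cut-offs) or as below that threshold, which covers both silent increases and milder worsening.
- Report both grades by arm.

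Simply defining *asymptomatic* as below both thresholds would give the same count, but it would label patients with up to 3 points of NIHSS worsening as free of symptoms. Grading avoids that.

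The cost is two matching text edits and one eCRF field. NIHSS and GCS are already taken at every visit, and CT is already done at 24 hours and 6 months in both arms, so no new assessment is needed. The reported recurrence rate may be higher than under the literal rule. If the sponsor always meant every confirmed increase to count, the edit changes no event count and only removes the ambiguity.

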2 BACKGROUND AND RATIONALE

Spontaneous supratentorial intracerebral hemorrhage (SSICH) is the second most common form of stroke, accounting for roughly 9-27% of all strokes and affecting more than 5 million people worldwide annually (approx. 2500 cases in Switzerland annually)[3]. Mortality rates are high with a range of 40-45%[4]. Patients surviving an SSICH mostly have very poor Health Related Quality of Life (HRQoL) and serious neurological deficits resulting in great burdens for them, their relatives and the social system[5-7].

Primary brain injury in SSICH occurs due to intra-axial bleeding causing mass effect and destruction of brain tissue[8]. Secondary mechanisms of brain injury are the local decay of hemoglobin, causing further brain damage due to its toxicity and delayed brain edema[9]. As such, the hematoma volume plays a vital role, as larger hematoma volumes lead to poorer outcome[10].

Treatment options for SSICH aim to stop enlargement of the hematoma volume or evacuation of the hematoma volume itself[11]. They consist of either, best medical treatment (a combination of medical blood pressure control, intensive care and prevention of secondary complications, short BMT, considered the current gold standard of treatment, or open surgical hematoma evacuation. Both treatment arms, showed similarly low rates of good functional outcome and survival (Class of Recommendation 2a, Level of Evidence B)[11, 12]. Intensive blood pressure reduction to below 140mmHg showed minimal improvement of functional outcome (OR 0.87, $p=0.04$) and mortality rates (OR 0.75, $p=0.06$)[13, 14].

Surgical treatment options for SSICH can be divided into conventional craniotomy (CC) and minimally invasive surgery (MIS), including endoscopic surgery (ES) and stereotactic aspiration (SA)[11, 15]. The Surgical Treatment for Intracerebral Haemorrhage (STICH) I and II trials, failed to show significant superiority of open surgical removal of SSICH with CC compared to BMT for improved functional outcomes or mortality[16, 17].

MIS on the other hand seems to be a promising alternative to BMT and CC. Recent systematic reviews/meta-analysis suggested that MIS leads to markedly improved survival and favorable outcome rates compared to BMT, yet the most promising MIS technique remains elusive[18, 19].

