4.3.1 V1: Study inclusion, baseline assessment and treatment: up to 24 hours after symptom onset

Study eligibility criteria are confirmed and written informed consent is obtained from the patient. After informed consent was given, randomisation to the intervention or the control group will be conducted by a member of the study team through the CDMS SecuTrial®.

A clinical examination is performed including vital signs (resting blood pressure and heart rate, height, and weight), NIHSS, GCS, and mRS. Blood sampling for biomarkers will be obtained. Patient baseline data is acquired.

In the intervention group a study baseline CT scan (stability scan) is obtained 6 hours after the admission scan if surgical hematoma evacuation is started >6 hours after the admission scan. Endoscopic hematoma evacuation must be initiated within 24 hours according to the procedure described in 3.4.1 “Intervention group”. Surgical Baseline data is acquired.

Patients randomised to the control group will receive standard medical care according to the current guidelines as described in 3.4.2 “control group”.

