5.1.3 Planned statistical methods

The primary analyses are performed following the intention-to-treat principle. Additionally, per-protocol analysis will be performed for sensitivity analysis. We study the ratio of positive outcomes in both study arms by performing a Bayesian A/B test after every 40 additional patients, using the method described by Gronau et al.[53]. Data collection (and the periodical analysis of these data) will continue until a Bayes Factor of 10 (or 1/10) is achieved. The odds

ratio and its 95% credible interval will be reported. Covariates ICH volume, presence of intraventricular bleeding, do-not-resuscitate orders, location of hematoma and centre will be included in a Bayesian logistic regression model

Secondary analysis is performed on the secondary outcomes. For continuous variables, a Bayesian regression with normal error term is used, for time-to-event outcomes Bayesian cox-regression is used, and for binary variables Bayesian logistic regression is used. Statistical analysis is performed with R version 4.2.1 or higher (R core Team, 2022)[54]. A complete mRS shift analysis will be calculated.

In parallel to the Bayesian primary analysis, we will perform a frequentist test of proportions comparing study arm for the first 100 patients per study arm. In the ES arm, a number of explorative analyses are performed, studying the relation between hematoma location, hematoma size, and treatment outcome. In particular, for parameters measured over time, figures are created illustrating the development over time at both the patient level and group level.

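### The secondary outcome labelled an mRS shift analysis is defined as a continuous change from baseline, which is a different analysis from an ordinal shift

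*Protocol*

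**What the plan says.** Section 3.2 lists among the secondary outcomes the change of disability on the mRS, "from baseline to 6 months after intervention as a continuous variable (change from baseline, so called mRS shift analysis". Section 5.1.3 then assigns models by variable type: "For continuous variables, a Bayesian regression with normal error term is used". Later in the same paragraph it adds "A complete mRS shift analysis will be calculated", with no model named. No ordinal or proportional-odds model appears anywhere in the protocol.

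On the baseline, section 4.3.1 has the mRS scored at V1, after the bleed: "A clinical examination is performed including vital signs (resting blood pressure and heart rate, height, and weight), NIHSS, GCS, and mRS". Section 4.1 separately uses a pre-stroke mRS, excluding patients above 2. Section 3.2 does not say which of the two is subtracted.

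The protocol never states that death counts as mRS 6 in its own outcome. A 4-6 range for poor outcome appears only where section 5.1.2.1 describes a cited review. The synopsis outcome list omits the mRS change outcome altogether.

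**The concern.** A shift analysis asks whether the ordered 6-month distribution, from no symptoms to death, is moved in one arm relative to the other. Its usual summary is a common odds ratio. The analysis that follows from 3.2 and 5.1.3 instead estimates a difference in mean numeric change. These are different estimands under one label.

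Three things follow. A reader of the results will take the label at face value and misread the estimate. The normal model scores a move from 6 to 5 the same as a move from 1 to 0, a weighting the protocol does not justify. And an analysis plan that used a proportional-odds model, as the label suggests, would contradict the protocol's only definition; section 5.1.6 calls for an amendment when a deviation is substantial.

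**Working it through.** The protocol gives no power or sample size for this outcome, so there is no stated figure to reproduce. The checks below use assumed mRS distributions.

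**1. Equal steps.** If 10 of 100 patients move from mRS 6 to 5, the arm mean changes by 10 × (-1)/100 = -0.10. If 10 of 100 move from 1 to 0, it changes by the same -0.10. The normal model cannot tell these apart.

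**2. Which baseline.** Assume a control 6-month distribution over mRS 0-6 of 2/8/15/25/15/5/30%, which keeps the protocol's 50% at mRS 0-3. Its mean is 3.78.
- Acute V1 baseline of 3/4/5 in 10/40/50% (assumed): mean 4.40, so mean change = 3.78 - 4.40 = -0.62.
- Pre-stroke baseline of 0/1/2 in 60/25/15% (assumed): mean 0.55, so mean change = 3.78 - 0.55 = +3.23.

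The sign and meaning of the reported change therefore depend on an unstated choice. The contrast between arms does not: with a common odds ratio of 1.8 it is -1.20 - (-0.62) = -0.58 with the first and 2.65 - 3.23 = -0.58 with the second.

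**3. Power.** Inputs: 100 per arm (the maximum of 200 in section 5.1.2.4); assumed control mRS of 2/8/15/25/15/10/25%; common odds ratio 1.95, giving 66% at mRS 0-3 and 15% dead; acute baseline 3/4/5 in 15/35/50%; death scored 6; 3,000 simulated trials per row, so each figure is good to about one point.

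| Correlation of baseline with 6-month mRS | Normal test on change | Rank test on 6-month mRS | 6-month mRS adjusted for baseline |
|---|---|---|---|
| 0 | 68% | 76% | 75% |
| 0.3 | 78% | 77% | 80% |
| 0.5 | 83% | 75% | 83% |
| 0.7 | 89% | 76% | 90% |

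The reversal follows from the variances. Var(change) = Var(Y) + Var(B) - 2ρ√(Var(Y)·Var(B)), which falls below Var(Y) once ρ > ½√(Var(B)/Var(Y)). Here Var(Y) = 16.83 - 3.73² = 2.92 and Var(B) = 19.45 - 4.35² = 0.53, so the threshold is ½√(0.53/2.92) = 0.21. Adjusting for baseline matches or beats the change score in every row.

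At the protocol's own effect, 0.50 × 1.6 = 0.80 in the surgical arm, the odds ratio is (0.80/0.20)/(0.50/0.50) = 4, and both tests have at least 99.8% power at 100 per arm.

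**4. Survivors.** NIHSS change, MoCA and PROMIS are also declared continuous, and no value is assigned to patients who die. Under a bivariate-normal selection model the survivor mean is ρ·φ(c)/(1 - m), with m the mortality and c its normal quantile. For assumed mortality of 45% against 35% and ρ of 0.5 to 0.7, survivors in the surgical arm look 0.075 to 0.105 SD worse with no true effect on the score. With 55 and 65 survivors the standard error is √(1/55 + 1/65) = 0.18 SD.

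**The case against.** The normal model for the mRS comes from joining two sections, not from one explicit sentence. The separate statement that "A complete mRS shift analysis will be calculated" could be read as a full-distribution analysis whose model is left to the analysis plan. That is a fair reading of 5.1.3 alone. It fails because 3.2 says what the protocol means by the term, and 5.1.3 offers no other definition.

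It can also be said that the planned estimate is interpretable: under randomisation, and with death scored 6, the difference in mean change estimates the difference in mean 6-month mRS. That stands, and it limits the point to a wrong label and a questionable scale. V1 is headed as the baseline assessment, so the acute score is the likelier baseline; the text still does not say so.

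A reader might infer that the definition costs power. The documents do not support this: the loss needs acute severity to be nearly unrelated to outcome. A reader might also infer that survivor-only NIHSS, MoCA and PROMIS comparisons will make surgery look harmful. That is not supported either. A rule for deaths in these scores normally belongs in the analysis plan, which is not at hand, and the shift above is about half a standard error and rests on assumptions. The statement that "Mortality rates are high with a range of 40-45"% describes the disease, not this trial's selected population. Control mortality of 45% alongside the protocol's 50% at mRS 0-3 would leave only 5% at mRS 4-5.

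**Conclusion.** The point holds as an error of definition in one secondary outcome. Sections 3.2 and 5.1.3 together specify a normal-error regression on a numeric mRS change and call it a shift analysis. The analysis assumes equal steps up to and including death, does not identify its baseline, and leaves the score for death unstated.

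The consequence is for interpretation and the estimand. The primary outcome, a binary 6-month mRS, is unaffected, and in the assumed scenarios the type I error of the test on change stays near 5%. No general loss of power should be claimed.

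As a secondary note only: because section 3.1 aims to show better survival with surgery, between-arm results for NIHSS ("The change of focal neurological deficit measured by the NIHSS, from baseline to 6 months after intervention as a continuous variable"), MoCA ("Patient cognitive outcome as assessed by the MOCA® Test (continuous variable, final value") and PROMIS ("Patient and caregiver quality of life as assessed by the PROMIS® questionnaire (continuous variable, final value") will compare survivors unless the analysis plan says otherwise. The last two are final values, not changes.

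**What to change.** In sections 3.2 and 5.1.3, define this outcome as the 6-month mRS on 0-6 with death scored 6, compared between arms by Bayesian proportional-odds regression. Adjust for the covariates already named for the primary analysis and for baseline severity already collected, for example V1 NIHSS. Delete the reference to change from baseline, which also removes the question of which baseline mRS is meant. Add the outcome to the synopsis list so that the two agree.

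The change is wording only and needs no new data. The downside is that the effect becomes a common odds ratio, which relies on proportional odds; showing the full mRS distribution by arm lets readers judge that.

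For NIHSS, MoCA and PROMIS, label the results as comparisons among survivors and report them beside mortality. Giving death the worst rank is one alternative, not a required correction; it would fold mortality, already a separate secondary outcome, into three more endpoints.
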